# **STUDY PROTOCOL**

The study will be carried out to 20 candidates who want to participate free of charge in exchange for their testimony and their commitment to the study.

The treatment will be carried out with the only technology on the market from Capernergy Medical, with its C-400 equipment, approved and authorized by the Ministry of Health, with its own national and international patents.

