# **BRIEF DESCRIPTION OF THE PROJECT**

The burden of obesity has increased globally in recent decades and its association with insulin resistance and related cardio-metabolic problems. Radio frequency (RF) is a form of high-frequency electromagnetic energy that works by heating tissues. Its action aims to increase cellular metabolism. Its action aims to increase cellular metabolism. Frequencies around 1 MHz are used, which are more effective in the cell, but with high power, adjustable temperature and treatment area greater than 200 cm2, which mechanically destroys the adipose cells, without damaging the skin, blood, vessels, nerves or connective tissues.

The lymphatic system eliminates lidis, reducing tissue volume. Magnetic resonance imaging (MRI) has similar accuracy to CT scans, but with no exposure to ionizing radiation. The MRI method for quantifying abdominal adiposity is effective. Chronic inflammation that lasts a long time is characterized by the presence of lymphocytes, macrophages, proliferation of blood vessels and connective tissue, it is considered a feature of metabolic syndrome, characterized by secretion of inflammatory adipokines usually from adipose tissue, leptin, interleukin (IL-6), tumor necrosis factor  $\alpha$  (TNF- $\alpha$ ), monocyte chemoattractant protein 1 (MCP-1) and resistin. RNA markers involved in apoptotic processes revealed that tissue exposed to RF treatment demonstrated a pro-apoptotic reaction. Therefore, we propose to apply through four channels and four electrodes of 200 cm2 a powerful RF energy raising the temperature and thus reducing visceral fat, evaluating the biochemical parameters of inflammation of the adipocyte.

MAIN OBJECTIVE: To understand the effect of high-power resistive capacitive RF on the decrease of body fat and changes in biochemical markers linked to inflammation.

METHODOLOGY: at the inclusion visit, the patient will be given the information sheet (Annex 1) and, if they agree, they will be asked to sign the informed consent. We aim to declare a difference of 2 points or more as significant, taking the SD from published research that gives around 8.0 with a confidence level of 95%, a power of 80% and a correlation coefficient of 0.70 between the values of abdominal circumference before and after treatment. Noted by Duarte et al. in 2015. We have obtained by EPIDATA that 15 pairs are needed.

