#### METHODOLOGY

At the inclusion visit, the patient will be given the information sheet (Annex 1) and, if they agree, they will be asked to sign the informed consent. Once included in the study, they will be randomly assigned to one of the two study groups in order of consecutive inclusion.

The project will be presented to the Ethics Committee of the Autonomous University of Barcelona UAB.

SAMPLE SIZE CALCULATION

The aim of this study was to assess the difference between a decrease in the diameter of the abdominal circumference in a group of women, before and after radiofrequency treatment. The aim is to be able to declare a difference of 2 points or more as significant, taking the SD from published research that gives around 8.0 with a confidence level of 95%, a power of 80% and a correlation coefficient of 0.70 between the values of abdominal circumference before and after treatment. These are taken from the article published by Duarte et al. in 2015 (Duarte et al, 2015), and the following results are obtained according to EPIDATA: 15 pairs of data will then be taken: Before and after the application of RF.

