## [1] Sample size. Comparison for paired means.

Data:

Mean differences to be detected:	6.442
Standard Deviation of the differences:	8.221
Level of confidence:	95.0%
sults.	

Results:

Stat. Power (%)	Number of Pairs
80.0	15

Inclusion criteria:

- Men and women from 20 to 60 years old

- With Waist-Hip Index. Greater than: 0.84 normal for women. 94 normal for men.

- Body Mass Index that is defined as: Overweight: Between 25-29.9. Obesity: 30 or higher.

- Measurement of Visceral Fat per Inbody greater than 9, which is what is considered Normal.

- Signed informed consent (Annex 1).

Exclusion Criteria:

- Contraindication to the use of radiofrequency: pregnancy, metal prostheses, active infection.

- Patients with a history of cancer, chemotherapy and radiotherapy treatments.

- Not having diabetes or metabolic disease.

MEASUREMENTS

Body Mass Index, Waist-t-Hip ratio and visceral fat:

Body Mass Index is calculated as follows: Body Weight (Kg) ÷ (Height in cm)2

Waist-to-Hip Ratio: According to World Health Organization guidelines, the waist should be measured at the midpoint between the last palpable rib and the top of the iliac crest (upper edge of the pelvis). The hip should be measured at the point of maximum circumference, i.e. the point where the buttocks reach maximum width. Both measures should be taken immediately after the air in the lungs is exhaled. It is important to keep your feet together and your arms in a normal position next to your body. It is advisable to take each measure twice and repeat it if different results are obtained (WHO 2008). The caliper takes the thickness of the abdominal wall at 5 cm in an oblique line towards the navel on the right and left side.

The visceral fat value: will be measured using, in addition to the MRI method, an Inbody electrical impedance equipment, in the first and last session.

TREATMENT

Each patient will have 4 active, automatic plates placed on the abdomen, two on the right side of the midline and two on the left side. Energy will be applied for 50 minutes, controlling the temperature. Subsequently, 15 minutes of Capacitive and Resistive manual electrodes will be applied to the abdomen, simultaneously, 20 minutes of Lymphatic Drainage placing one active plate in the foot and the other in the lumbo-dorsal area. You will be informed that you will only feel comfortable warmth. Five sessions will be applied from Monday to Friday resting Saturday and Sunday, for 2 weeks. Total 10 sessions.

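### The 15-pair, 80%-power calculation is for one group measured before and after; it is not reconciled with randomisation to two groups, treatment of every patient, or 20 candidates

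*Combined protocol and SAP*

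**What the plan says.** All of the following is in the combined protocol and SAP.

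- **Required size.** The Brief Description says "We have obtained by EPIDATA that 15 pairs are needed". The sample-size paragraph of the Methodology says "15 pairs of data will then be taken: Before and after the application of RF".
- **Calculation table.** The table is headed as a comparison of paired means. It reads "Mean differences to be detected: 6.442", with an SD of the differences of 8.221, 95% confidence, 80% power and 15 pairs.
- **Number of participants.** The Study Protocol section says "The study will be carried out to 20 candidates".
- **Groups.** The opening paragraph of the Methodology says that, once included, "they will be randomly assigned to one of the two study groups in order of consecutive inclusion". No group sizes, allocation ratio or description of a second group are given.
- **Who is treated.** The Treatment section says "Each patient will have 4 active, automatic plates placed on the abdomen".
- **Analysis.** The statistical analysis section lists Student's t-test for both paired and independent samples. It does not say which groups or outcome the independent-samples test compares.
- **Loss to follow-up.** No dropout rate is stated, and no sentence links 15 to 20.

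**The concern.** A paired calculation sizes one comparison: the mean change, before to after, in people who receive radiofrequency. Randomisation to two groups and an independent-samples test point to a different one: the change in one group against the change in the other. That comparison has a larger standard error for the same number of people, and nothing in the plan sizes it.

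The statements also conflict as they stand. If every patient receives the same treatment, the randomisation sentence has no stated purpose. If one group is a comparator, the sentence treating each patient does not describe it. A reader cannot tell how many people will receive radiofrequency, how many complete pairs are expected, or which comparison the 80% refers to. These facts decide whether the trial reports an uncontrolled before/after change or a randomised effect, and how a non-significant result should be read.

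**Working it through.** **Inputs.** From the calculation table: difference d = 6.442 and SD of differences s = 8.221, so d/s = 0.7836. The 95% confidence is taken as two-sided alpha 0.05; sidedness is not stated, but this choice reproduces the plan's figure.

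**1. The plan's own figure.** For a paired t-test with n pairs, the noncentrality is (d/s)√n on n − 1 degrees of freedom. At n = 15 it is 0.7836 × √15 = 3.03, against a critical t of 2.145, and power is 80.6%. At n = 14 power is 77.3%. So 15 is the smallest n reaching 80%, and the table reproduces. (The normal approximation gives 12.8, rounded up to 13.)

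**2. Paired power at other numbers of treated pairs.**

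| Complete treated pairs | How it could arise | Noncentrality | Power |
|---|---|---|---|
| 20 | all 20 treated and measured twice | 3.50 | 91.3% |
| 15 | the number required; also 20 split 15:5 | 3.03 | 80.6% |
| 10 | 20 split 1:1, one group untreated | 2.48 | 59.9% |

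**3. Between-group comparison of changes.** The documents give no inputs for this, so assumptions are needed: the second group is untreated, its mean change is zero, and both groups have an SD of change of 8.221. The between-group difference is then 6.442. The noncentrality is d / [s√(1/n₁ + 1/n₂)] on n₁ + n₂ − 2 degrees of freedom.

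| Split | Noncentrality | Power |
|---|---|---|
| 10 v 10 | 6.442 / (8.221 × √0.2) = 1.75 | 38.2% |
| 15 v 5 | 6.442 / (8.221 × √0.2667) = 1.52 | 30.1% |
| 15 v 15 | 6.442 / (8.221 × √0.1333) = 2.15 | 54.5% |

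With 20 people in total, 1/n₁ + 1/n₂ is smallest at 10 v 10, so 38% is the most any split can give. For 80%, the t-based calculation gives 79.1% at 26 per group and 80.7% at 27, so 27 per group, or 54 in all.

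**4. Could 20 be 15 plus an allowance?** 15/0.75 = 20, so a 25% loss would connect the two numbers. That rate is an assumption; it appears nowhere in the documents.

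**5. Dependence on the table's inputs.** The text plans for a difference of 2 points, an SD of about 8.0 and a correlation of 0.70. These imply an SD of differences of 8.0 × √(2 × (1 − 0.70)) = 6.20. On those inputs, paired power is 21.4% at 15 pairs and 27.8% at 20, and 80% needs 78 pairs. Every power figure in steps 1 to 3 therefore holds only if the table, not the text, states the planning effect.

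**The case against.** The strongest reply is that this is a single-arm before/after study and the randomisation sentence is a stray. Much in the documents supports that. The Treatment section gives the active plates to each patient, the objectives are worded as before against after, and the treatment and cost terms in the Study Protocol section apply to all participants alike. On that reading nothing is underpowered on the table's inputs: 15 is the minimum, 20 exceeds it, and power is 91% if all 20 complete.

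Most of this stands, and it limits the point in three ways.

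- A reader might infer that 15 against 20 undermines the 80%. It does not. Recruiting more than the required number is ordinary; what is missing is a sentence linking the two.
- A reader might infer that randomisation must leave only 10 treated pairs, or that the 15 would be halved to 7 or 8. The documents do not support either. Ten requires an equal split and an untreated group, neither of which is stated. Halving the 15 contradicts the Methodology, which defines them as pairs taken before and after radiofrequency.
- The between-group figures reuse a before/after difference and assume no change in the second group. No objective states a between-group comparison.

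The reply does not remove the conflict. The text does randomise to two groups and does list an independent-samples test. If the single-arm reading is right, the randomisation sentence is wrong; if it is not, the calculation does not size the comparison.

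**Conclusion.** The plan is wrong as written: it contains a one-group sample-size calculation and a two-group allocation, and does not say which describes the trial. The arithmetic of the 15 pairs is sound on the table's inputs.

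The size of the problem depends on the reading. If all 20 are treated, there is no power shortfall on those inputs, only statements to reconcile. If there is an untreated comparison group, the 80% does not apply to the between-group comparison, which has at most 38% power with 20 people under the assumptions in step 3. In that case the paired test keeps 81% only if at least 15 treated people supply complete pairs. A 15:5 split does that at the price of 30% between groups; a 1:1 split leaves 60% for the paired test.

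It would go too far to say that the trial cannot deliver its stated power. The documents do not fix the allocation or the content of the second group. They leave the reach of the 80% undefined.

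**What to change.** 1. First resolve the conflict between the table's inputs (6.442; SD of differences 8.221) and the text's (2 points; SD about 8.0; r = 0.70). Every restated power figure depends on it.
2. State one number recruited and the number of complete treated pairs expected. Say whether 20 includes an allowance for loss and, if so, at what rate.
3. Then choose one description and reconcile the Methodology, Treatment and analysis sections with it:
   - *Single-arm before/after study.* Delete the two-group randomisation sentence, and say what the independent-samples test is for or remove it.
   - *Two groups.* Define the second group, its size and the allocation ratio. Limit the 80% to the paired comparison, provided at least 15 treated pairs are expected; otherwise restate it. Give the power of the between-group comparison and, with 20 people, label that comparison exploratory.

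Cost: wording and restated power figures, with no extra patients. Only a between-group comparison with 80% power would need more, about 27 per group on the table's inputs and the assumptions in step 3.

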## OBJECTIVES

MAIN OBJECTIVE.

- To understand the effect of high-power resistive capacitive radiofrequency on the decrease of body fat and changes in biochemical markers linked to inflammation.
  SIDE OBJECTIVES.
  - 2. To assess the role of radiofrequency in reducing abdominal fat.
  - 3. To assess and compare the decrease in abdominal circumference measured by anthropometric tape measure, Body Mass Index, Waist-to-Hip Ratio and skinfold before and after RF treatment.
  - Evaluate changes in Human IL-6, Human TNF-alpha, Human-Leptin, Human-Adiponectin, Human-Resistin, C-reactive protein values before and after RF sessions. Evaluar y comparar el impacto de la calidad de vida antes y después del tratamiento con radiofrecuencia.
  - 5. To assess and compare the impact of quality of life before and after radiofrequency treatment.

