# + info: http://capenergy.com/es/product-detail/

The treatment will consist of the application of diathermy, providing the effects of tecartherapy, which are perceived as endogenous heat on the treated area.

The treatment will be individual and exclusive, with maximum discretion, in a quiet and relaxed environment.

The duration of the treatment will be 5 weeks, where 10 sessions will be carried out, 2 per week.

The cost of the treatment is valued at 1000 euros. Participants agree to start and end the study. In case of abandonment, they must reimburse the cost of the treatment.

The cost of the tests carried out will not be passed on to the patients, it is valued at 212 euros.

On the part of the professionals of INNEOTERAPIA, the treatment protocol established in the study will be applied.

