# **Objective of the study:**

- 🛠 Main
  - Decrease in body fat and biochemical markers.
- Secondary
  - Reduction in abdominal fat.
  - Decrease in abdominal circumference, body mass index.
  - Changes in glycemia, cholesterol and triglycerides.
  - Evaluate and compare the impact of quality of life.

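### Free treatment is given in exchange for an undefined testimony, which adds an avoidable risk of selection and reporting bias to the before-after quality-of-life objective

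*Combined protocol and SAP*

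**What the plan says.** The Study Protocol section sets the number and the terms of recruitment: "The study will be carried out to 20 candidates", described as "candidates who want to participate free of charge in exchange for their testimony and their commitment to the study". The following section (headed + info) gives the value of what is exchanged: "The cost of the treatment is valued at 1000 euros". It adds a repayment term: "In case of abandonment, they must reimburse the cost of the treatment".

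Quality of life is an objective in both parts of the document. The Objectives section lists it as a side objective: "To assess and compare the impact of quality of life before and after radiofrequency treatment". The later Objective of the study section lists it as secondary: "Evaluate and compare the impact of quality of life". No instrument, assessor or timing beyond before and after is given.

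On design, the Methodology section says that patients, once included, "they will be randomly assigned to one of the two study groups in order of consecutive inclusion". The Treatment subsection then describes active plates for every patient and no other regimen. The + info section says the effects of the treatment are ones "which are perceived as endogenous heat on the treated area".

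**The concern.** Testimony is listed alongside commitment to the study, so it reads as something owed beyond attending and supplying data. The supplied text does not say what it consists of, who receives it, when it is given, or whether it is kept apart from outcome assessment.

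Two routes to bias follow. At entry, people willing to give a testimony in return for free treatment may be more favourable to it than other eligible people. At the end, someone who owes a testimony may rate quality of life more favourably than they otherwise would. The second route acts on participants who complete. It is therefore distinct from the repayment clause, which acts on who stays, and removing that clause would leave this problem in place.

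What is at stake is the reading of the quality-of-life result. The objective is a within-person comparison, so a shift in reporting between the first and last rating goes straight into the estimated change. Because the recruitment term covers all 20 candidates, there is no unaffected subset to compare with.

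**Working it through.** **Step 1: is the exchange stated or inferred?** It is stated. The Study Protocol section ties free participation to testimony, and the + info section prices the treatment at 1000 euros. What the testimony contains is not stated.

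**Step 2: can it reach an outcome?** Quality of life is an objective in two places. No instrument is named; I assume it is rated by the participant. Participants feel the heat, the Treatment subsection gives every patient active plates, and no sham or masking is described. That they know they are treated is an inference from this silence, not a statement in the plan. Two randomised groups are mentioned, but no second treatment is described, and both versions of the objective can be met by a before-after comparison.

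**Step 3: which outcomes are exposed?** Quality of life is exposed directly. MRI fat volumes and the laboratory markers do not depend on what the participant chooses to report, so they are much less exposed.

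**Step 4: does the plan size this objective?** No. Its only calculation concerns abdominal circumference. With the software inputs (mean difference 6.442, SD of differences 8.221, two-sided 5%, 80% power), the normal approximation is

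(8.221 × (1.960 + 0.842) / 6.442)² = 12.8, so 13 pairs.

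The paired t-test calculation with the noncentral t distribution gives 15 pairs, with 80.6% power. The stated 15 is reproduced. It says nothing about quality of life, for which the documents give no effect size, SD or bias size.

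**Step 5: illustration of how far a shift could matter.** Suppose radiofrequency has no effect on quality of life and the mean rating moves by b SDs of the change score through reporting alone. A two-sided paired t-test at 5% is then significant with probability P(|T| > t), where t is the 97.5% point on n − 1 degrees of freedom and T is noncentral t with noncentrality b√n. For example, b = 0.3 and n = 20 gives 0.3 × √20 = 1.34.

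| Assumed shift b (SD of change) | n = 15 | n = 20 |
|---|---|---|
| 0.1 | 7% | 7% |
| 0.2 | 11% | 14% |
| 0.3 | 19% | 25% |
| 0.5 | 44% | 56% |

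Both sample sizes are shown because the plan gives 15 pairs in one place and 20 candidates in another. Every value of b is an assumption; with b = 0 the figure is the nominal 5%.

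**The case against.** The strongest reply is that too much can be read into one word. A reader might infer that participants must publicly endorse the device. The documents do not say that. The text is a translation, with one sentence still in Spanish, and the word may mean no more than reporting one's experience to the study. The device is named in the next sentence, which makes the promotional reading plausible, but that sentence calls it the only technology on the market from its manufacturer, which is weaker than calling it the only one on the market. The + info section also promises discretion, which sits poorly with presenting participants as cases. The consent pages and some sections were not in the supplied text and may define the term. This objection stands against any claim about what the testimony is. It does not remove the condition itself, which is current text.

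Second, two randomised groups are mentioned, and a shift shared by both would partly cancel in a between-group comparison. That is correct in principle. However, no comparator treatment is described, and a before-after objective would not benefit from the cancellation.

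Third, the reach is narrow and the result is confounded anyway. Quality of life is one secondary objective, and the candidate criteria already require everyone to follow a diet and exercise pattern. Both statements stand. They limit the importance of the point and what the fix can achieve, but they are no reason to keep an additional source of bias that is easy to remove.

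A reader might also infer that the testimony raises lifestyle adherence and so inflates the circumference change. Nothing in the documents supports this, since diet and exercise are already required of every participant for other reasons.

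**Conclusion.** The point holds as a risk. The plan makes free treatment valued at 1000 euros conditional on a testimony it does not define, and it describes no masking or comparator treatment that would protect a before-after quality-of-life rating. The expected direction of any shift is toward improvement, but neither its existence nor its size can be shown from the documents. The 7% to 56% range at n = 20 rests wholly on assumed shifts of 0.1 to 0.5 SD.

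The conclusion assumes that quality of life is self-rated, that participants know they are treated, and that no omitted page already makes the testimony optional. The documents do not support concluding that the quality-of-life result is demonstrably biased, or that the main objective is compromised. This is a cheap improvement to a secondary objective.

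**What to change.** In the Study Protocol section, and in the matching participant agreement, remove testimony as a condition of free participation and state that taking part carries no obligation to give one. If testimonials are wanted, request them under a separate voluntary consent after the participant's last outcome has been recorded. Have the quality-of-life form self-completed without treating staff present. If an omitted page already defines the testimony, reconcile it with this section.

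The cost is small but not nil: a few sentences, one extra consent form, a minor change in how the form is completed, fewer or later testimonials, and possibly slightly slower recruitment. The sample-size calculation is unaffected. The change removes one source of bias only: with diet and exercise required of everyone, the before-after change in quality of life still cannot be attributed to radiofrequency, and the report should say so.
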